1.3.2. SECONDARY EFFICACY ANALYSES

1.2.2.1 OS

At 6 months the estimated OS was xx % (with xx% CI xx-xx), at 9 months it was xx % (with xx% CI xx-xx), at xx months it was

The median of OS was xxx months (with xx% CI xx-xx)

Table 25. OS estimated survival ratio

Overall Survival	Events (% , total N)	Patients at risk	% estimated cumulative survival ratio	CI 95%
At 6 months				
At 9 months				
At 12 months				
At 18 months				
.....				

[figure not shown]
Note: Estimated using Kaplan-Meier product-limit method

Table 26. Median/mean OS (estimated by Kaplan-Meier)

	Median (months)	CI 95%	Mean	CI 95%
Overall Survival				

Note: Estimated using Kaplan-Meier product-limit method

Figure 2. Overall Survival

In those patients who died (n=xx), the median of follow-up was xx months.

Table 27. Time until exitus (only deaths)

Overall	Overall (N=xx)
Time until Exitus	
N	
Mean (95%CI)	
SD	
Median (95%CI)	
Range	

In overall, the median of follow-up was xx months (minimum xx months and maximum of xx months).

Table 28. Time of follow-up (all patients)

Overall	Overall (N=xx)
Time until Exitus	
N	
Mean (95%CI)	
SD	

Overall	Overall (N=xx)
Median	
(95%CI)	
Range	

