1.2. EFFICACY ANALYSES

1.2.1. PRIMARY EFFICACY ANALYSES: PFS

At 6 and 9 months the estimated PFS was 21.23% (with 95% CI 11-40.97), at 12 months it was 16.99% (with 95% CI 7.71-37.43) and from 18 to 48 months it was 11.32% (with 95% CI 3.68-34.86).

The median of PFS was 2.84 months (with 95% CI 2.71-5.39).

Table 22. PFS estimated survival ratio

Progression Free Survival	Events (% total N)	Patients at risk	% estimated cumulative survival ratio	CI 95%
At 6 months				
At 9 months				
At 12 months				
At 18 months				
At 24 months				
At 30 months				
At 36 months				
At 42 months				
At 48 months				

[figure not shown]
Note: Estimated using Kaplan-Meier product-limit method

Table 23. Median/mean PFS (estimated by Kaplan-Meier)

Progression Free Survival	Median (months)	CI 95%	Mean	CI 95%

Note: Estimated using Kaplan-Meier product-limit method

Figure 1. Progression Free Survival

In the 28 patients with PD, the median until progression was 2.8 months.

Table 24. Time until PD/exitus (only pts with event)

Overall	Overall (N=xx)
Time until PD/Exitus	
N	
Mean (95%CI)	
SD	
Median (95%CI)	
Range	

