1.2.2. ADEVERSE EVENTS

The most frequent adverse event (any grade) were xxxxx (xx%, n=xx)....

Table 43. Frequencies of all adverse events

Adverse event	N	%
EXAMPLES:		
Neutrophil count decreased		
Fatigue		
Platelet count decreased		
Anaemia		
.....		

%: calculated respect the total number of patients (N=34)

The most frequent adverse events, (at least in 10% of the patients, n=xx), are reported in the following table:

Table 44. Most frequent adverse events

	N	%	
Specify Adverse events.	No	10	29.4%
	Yes	24	70.6%
EXAMPLE: Fatigue	Total	34	100.0%
.....	No	14	41.2%
	Yes	20	58.8%

Total	34	100.0%
--------------	----	--------

The most frequent adverse events with their respective grades are reported in the following table:

Table 45. Most frequent adverse events with grades

	No		G1		G2		G3		G4		Total	
	N	%	N	%	N	%	N	%	N	%	N	%

Specify Adverse events.

EXAMPLE: Fatigue

.....

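### SAP Table 28 appears to take median follow-up over observed times including deaths, so it largely restates survival and understates follow-up; event-only Tables 24 and 27 should not carry inferential estimates

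*SAP*

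**What the plan says.** In the SAP's OS subsection (1.2.2.1), the follow-up output is "Table 28. Time of follow-up (all patients"). Its shell lists N, mean with 95% CI, SD, median with 95% CI and range. The row header refers to time until exitus, although the title covers everyone and Table 30 provides for living patients. The accompanying sentence promises a median, a minimum and a maximum. Tables 25 and 26, just above, carry a Kaplan-Meier footnote; Table 28 does not, and reverse Kaplan-Meier is not mentioned.

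Two further tables are restricted to patients with the event: "Table 24. Time until PD/exitus (only pts with event") for PFS and "Table 27. Time until exitus (only deaths") for OS. Both ask for means and medians with 95% CIs. The sentence introducing Table 27 calls the median time among those who died a median of follow-up.

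The PFS text gives both kinds of median: "The median of PFS was 2.84 months (with 95% CI 2.71-5.39") by Kaplan-Meier, and "In the 28 patients with PD, the median until progression was 2.8 months". Kaplan-Meier medians and means are already provided in Table 23 (PFS) and Table 26 (OS).

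**The concern.** Median follow-up is there to tell the reader how long patients could have been observed, and so how mature the OS data are. If a patient who dies at month 5 contributes 5 months of follow-up, the statistic falls as mortality rises, whatever the calendar time since enrolment. With many deaths it comes close to median survival under another name.

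The event-only tables raise a separate and smaller issue. They condition on having had the event, so patients still event-free at last contact, who include the longest times, are left out. Printed with 95% CIs beside the Kaplan-Meier results, they can be read as alternative estimates of PFS and OS.

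**Working it through.** **1. The PFS curve, to see who Table 24 omits.** Inputs: 34 patients ("calculated respect the total number of patients (N=34")), 28 events, and 7 patients with PFS of at least 9 months (SAP Table 53). One sequence reproduces every stated rate: 1 event, 1 censored, 25 events, 2 censored, 1 event with 5 at risk, 1 censored, 1 event with 3 at risk, 2 censored. That makes 28 events and 6 censored. Limits are S × exp(±1.96√V), where V is the Greenwood sum of 1/[n(n−1)].

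- 6 and 9 months: S = 33/34 × 7/32 = 0.2123; V = 1/(34×33) + (1/7 − 1/32) = 0.1125; limits 11.00% to 40.97%. Stated: "At 6 and 9 months the estimated PFS was 21.23% (with 95% CI 11-40.97").
- 12 months: S = 0.2123 × 4/5 = 0.1699; V = 0.1125 + 1/20 = 0.1625; limits 7.71% to 37.43%. Stated: "at 12 months it was 16.99% (with 95% CI 7.71-37.43").
- 18 to 48 months: S = 0.1699 × 2/3 = 0.1132; V = 0.1625 + 1/6 = 0.3292; limits 3.68% to 34.86%, as stated.

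Table 24 therefore leaves out 6 of 34 patients. Only 2 of the 7 with PFS of 9 months or more had an event, so 5 of those 7 are omitted.

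**2. Effect on the PFS summaries.** The Kaplan-Meier median is the 17th event: S is 33/34 × 17/32 = 0.516 after the 16th and 33/34 × 16/32 = 0.485 after the 17th. The event-only median lies between the 14th and 15th events. The stated figures differ by 2.84 − 2.8 = 0.04 months. The mean is affected much more. Three illustrative sets of event times that fit the curve give event-only means of 2.5, 3.5 and 4.7 months, against Kaplan-Meier means restricted to 48 months of 8.0, 8.9 and 10.0. The tail from 18 to 48 months alone adds 0.1132 × 30 = 3.4 months to the restricted mean.

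**3. Size of the Table 28 problem.** Median OS is blank in the SAP, so a range is assumed. Other inputs: first inclusion in Q4 2015 and 28 months' recruitment (protocol 3.7), and database closure on 10-10-2019 (SAP section 1). Mid-Q4 2015 to October 2019 is about 47 months, and 47 − 28 = 19, so potential follow-up is taken as uniform on 19 to 47 months. OS is exponential, with no other loss.

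- Reverse Kaplan-Meier targets median potential follow-up: (19 + 47)/2 = 33 months.
- The plain median solves P(T > t) × P(C > t) = 0.5. Nobody is censored before 19 months, so for OS medians of 12 and 18 months the solution is the OS median itself. For 24 months, at t = 21.2: exp(−0.693 × 21.2/24) × (47 − 21.2)/28 = 0.542 × 0.921 = 0.50.

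Simulating 34-patient trials under these assumptions gives (times in months; the last column averages over trials):

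| Assumed OS median | Mean number alive | Plain median | Reverse KM median | Reverse KM not estimable | Deaths-only vs KM median OS |
|---|---|---|---|---|---|
| 6 | 1 | 6 | 27 | 45% | 5.8 vs 5.8 |
| 9 | 3 | 9 | 31 | 16% | 8.0 vs 8.8 |
| 12 | 6 | 12 | 33 | 4% | 9.5 vs 11.8 |
| 18 | 10 | 18 | 33 | under 1% | 11.5 vs 17.7 |
| 24 | 13–14 | 21 | 33 | 0% | 12.7 vs 23.9 |

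With potential follow-up of 17–45 or 20–48 months instead, reverse Kaplan-Meier gives about 31–34 months for OS medians of 12 to 24 months, and the plain median about 12, 18 and 20–22. At an OS median of 12 months, 95% of the estimable reverse Kaplan-Meier values lie between about 24 and 44 months.

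**The case against.** Several points on the other side have force.

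- **The method is inferred.** No formula is given, and observed time on study is a legitimate descriptive quantity. The first part stands as a caveat. But SD and range are raw-data statistics, the Kaplan-Meier footnote is absent, and time to death is called follow-up in the sentence for Table 27, so the plain reading is much the likelier one. The wrong row label needs no inference.
- **Maturity can be judged elsewhere.** Table 25 gives OS events and numbers at risk, Table 30 the numbers alive and dead, Figure 2 the OS curve and Figure 8 a swimmer plot. This limits the harm, but the sentence a reader will quote is still the median follow-up.
- **Event-only tables are labelled as such** and follow the Kaplan-Meier results. A reader might infer that they too misstate data maturity, or that the PFS result is biased. The documents support neither: time among patients with the event is a different descriptive quantity, and the stated PFS medians differ by 0.04 months.
- **The OS gap depends on the assumed survival.** Protocol 4.1 describes survival after failure of standard treatment as a few months. At an OS median of 6 months the deaths-only and Kaplan-Meier medians agree. This stands for Table 27; for Table 28 a shorter OS widens the gap.
- **The replacement has a cost.** Reverse Kaplan-Meier draws its events from the living patients, so it is unstable when there are few. This stands, and it is why the observed range and the number alive should be kept beside it.

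**Conclusion.** The point holds as a minor improvement to reporting. On the likely reading of Table 28, its median would understate potential follow-up by about 12 to 21 months (33 − 21 to 33 − 12) for assumed OS medians of 24 down to 12 months, and would mostly repeat median survival. This rests on the inferred method, uniform accrual on the planned schedule, exponential OS and no loss to follow-up.

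Tables 24 and 27 are a lesser matter. Their effect on the PFS median is negligible. Their effect on the PFS mean is large: roughly half or less of the restricted Kaplan-Meier mean in the illustrations. Their effect on median OS runs from nil at an OS median of 6 months to about 11 months at 24. Because they print CIs, they should not stand as second estimates.

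It would go too far to conclude that the efficacy results are compromised. PFS and OS are estimated by Kaplan-Meier, the protocol's success rule (section 10.3) counts patients alive and progression-free at 6 months, and neither uses these tables.

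**What to change.** - **Table 28:** state that median follow-up is computed by reverse Kaplan-Meier, with deaths censored and end of follow-up as the event, and give its 95% CI. Report the observed minimum and maximum and the number still alive beside it. If the median is not reached, say so and rely on the range and number alive. Relabel the row as follow-up time.
- **Text for Table 27:** describe the deaths-only figure as time to death, not follow-up.
- **Tables 24 and 27:** drop them with their sentences, or mark them as descriptive, events only, and remove the CIs, so that Tables 23 and 26 hold the only inferential estimates.

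The cost is a few lines of SAP wording and code, with no new data. The one drawback is the imprecision of reverse Kaplan-Meier when few patients are alive.

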1.2.2.2 RESPONSES

13 patients (38.2%, with 95% CI 21.9-54.6), reached clinical benefit (all were Stable Disease).

Table 29. Best response and Clinical benefit rate

		N (% , 95% CI)
Best response rate	CR	
	SD	
	PD	
	No evaluated	
	Total	
Clinical benefit rate	No	
	Yes (CR or PR or SD)	
	No evaluable	
	Total	

In xx patients (xx%) the reason to end of treatment was PD; xx patients (xx%) were alive at the end of follow-up.

Table 30. Status at end of study

		N (%)
Current status	End of treatment due to patient decision and patient is alive at end of follow-up	
	End of treatment due to PD and patient is alive at end of follow-up	
	End of treatment due to PD and patient is exitus	
	End of treatment but reason not reported and patient is exitus	
	End of treatment due to lack of clinical benefit and patient is alive at end of follow-up	
	On treatment	
	Total	
End of treatment reason	PD	
	Toxicity (with PD)	
	Patient decision	
	On treatment	
	No clinical benefit	
	Total	
Status at end of follow-up	Alive	
	Exitus	
	Total	

1.2.2.3 RANO EVALUATION

xx patients (xx%) presented PD in RANO evaluations, xx (xx%) of them in the 2nd RANO, x (xx%) the 3rd, x (xx%) in the 5th and x (xx%) in the 6th.

Table 31. RANO Evaluation (I)

	N	%
RANO evaluation 2 without PD in RANO		
with PD		
3		
5		
6		
Total		
Reason of PD with RANO		
Example:		
T1-Gd+; T2-FLAIR: / New lesions: New appearance/ Corticoids evolution (last 5 days): Stable/ Clinical evaluation (neurological): Stable		
...		
Total		

Table 32. RANO Evaluation (II)

		N	%
	NA or not reported		
T1Gd+ (PD RANO)	Decrease <5% or Increase < 25%		
	Increase >= 25%*		
	Total		
	NA or not reported		
T2/FLAIR (PD RANO)	Increase		
	Stable		
	Total		
	NA or not reported		
New lesions (PD RANO)	New appearance		
	No		
	Total		
	NA or not reported		
Corticoids evolution (PD RANO)	Decrease		
	Increase		
	No corticoids		
	Total		
	NA or not reported		
Clinical evaluation (PD RANO)	Stable		
	Worsening		
	Total		

Table 33. List of patients with RANO progressions with details
Reason of PD with RANO

Patient number	Evaluation RANO con PD	Reason of PD with RANO
1		Example: T1-Gd+: Increase \geq 25%/ T2-FLAIR: Stable/ New lesions: No/ Corticoids evolution (last 5 days): No corticoids/ Clinical evaluation (neurological): Stable
2		
...		

1.2.2.4 USE OF CORTICOIDS

x patients (xx%) reported use of corticoids.

[figure not shown]
Table 34. Use of Corticoids

	N	%
Receive corticoids during treatment (cycles)	No	
	Yes	
	Total	
Changes in corticoids doses from baseline (during treatment cycles)	No	
	Increased	
	Increased with posterior decrease	
	Decreased	
	Stable	
Total		

Table 35. List of patients receiving corticoids and Follow-up of dosage

Patient number	Receive corticoids during treatment (cycles)	Changes in corticoids doses from baseline (during treatment cycles)	C1 D1	C1 D15	C2 D1	C2 D15	C3 D1	C4 D1	C5 D1	C6 D1	C7 D1	C8 D1	C9 D1	C10 D1	C11 D1
1	Yes	Example: Decreased/Increased/Stable													
2															
3														

Figure 3. Use of corticoids

1.1.1.1 EVOLUTION OF MINIMENTAL TEST

The results of the minimental test for each patient (when available), is reported in the following table.

Table 36. Minimental Test: Results for each patient

Patient number	Baseline	C2 d1	C3 d1	C4 d1	C5 d1	C6 d1	C7 d1	C8 d1	C9 d1	C10 d1	C12 d1	C13 d1	C14 d1	C15 d1	C16 d1	C17 d1	C18 d1	C19 d1	C20 d1	C21 d1	C22 d1	C23 d1	End of treatment	
....																								

Table 37. Minimental Test: Summary in each visit

	N	Mean (SD)	Median (Min-Max)
Test Minimental (baseline)			
Test Minimental (cycle 2 d1)			
Test Minimental (cycle 3 d1)			
Test Minimental (cycle 4 d1)			
Test Minimental (cycle 5 d1)			
Test Minimental (cycle 6 d1)			
Test Minimental (cycle 7 d1)			
Test Minimental (cycle 8 d1)			
Test Minimental (cycle 9 d1)			
Test Minimental (cycle 10 d1)			
Test Minimental (cycle 12 d1)			
Test Minimental (cycle 13 d1)			
Test Minimental (cycle 14 d1)			
Test Minimental (cycle 15 d1)			
Test Minimental (cycle 16 d1)			
Test Minimental (cycle 17 d1)			
Test Minimental (cycle 18 d1)			
Test Minimental (cycle 19 d1)			
Test Minimental (cycle 20 d1)			
Test Minimental (cycle 21 d1)			
Test Minimental (cycle 22 d1)			
Test Minimental (cycle 23 d1)			
Test Minimental (end of treatment)			

Table 38. Minimental Test: Comparison between visits and baseline

	N	Mean (SD)	Median (Min-Max)	p-value ¹
Test Minimental (baseline)				
Test Minimental (cycle 2 d1)				
Test Minimental (baseline)				
Test Minimental (cycle 3 d1)				
Test Minimental (baseline)				
Test Minimental (cycle 4 d1)				
Test Minimental (baseline)				
Test Minimental (cycle 5 d1)				
Test Minimental (baseline)				
Test Minimental (cycle 6 d1)				
Test Minimental (baseline)				
Test Minimental (cycle 7 d1)				
Test Minimental (baseline)				
Test Minimental (cycle 8 d1)				
Test Minimental (baseline)				

Test Minimental (cycle 9 d1)

Test Minimental (baseline)

Test Minimental (cycle 10 d1)

Test Minimental (baseline)

Test Minimental (end of treatment)

1: Wilcoxon test

[figure not shown]

Figure 4. Minimental Test evolution

1.1.1.2 EVOLUTION OF BARTHEL INDEX

The results of the Barthel Index for each patient (when available), is reported in the following table.

Table 39. Barthel Index: Results for each patient

Patient number	Baseline	C2 d1	C3 d1	C4 d1	C5 d1	C6 d1	C7 d1	C8 d1	C9 d1	C10 d1	C11 d1	C12 d1	C13 d1	C14 d1	C15 d1	C16 d1	C17 d1	C18 d1	C19 d1	C20 d1	C21 d1	C22 d1	C23 d1	End of treatment	
....																									

Table 40. Barthel Index: Summary in each visit

	N	Mean (SD)	Median (Min-Max)
Barthel Index (baseline)			
Barthel Index (cycle 2 d1)			
Barthel Index (cycle 3 d1)			
Barthel Index (cycle 4 d1)			
Barthel Index (cycle 5 d1)			
Barthel Index (cycle 6 d1)			
Barthel Index (cycle 7 d1)			
Barthel Index (cycle 8 d1)			
Barthel Index (cycle 9 d1)			
Barthel Index (cycle 10 d1)			
Barthel Index (cycle 11 d1)			
Barthel Index (cycle 12 d1)			
Barthel Index (cycle 13 d1)			
Barthel Index (cycle 14 d1)			
Barthel Index (cycle 15 d1)			
Barthel Index (cycle 16 d1)			
Barthel Index (cycle 17 d1)			
Barthel Index (cycle 18 d1)			
Barthel Index (cycle 19 d1)			
Barthel Index (cycle 20 d1)			
Barthel Index (cycle 21 d1)			
Barthel Index (cycle 22 d1)			
Barthel Index (cycle 23 d1)			
Barthel Index (end of treatment)			

The Barthel Index result in each visit was compared with the baseline result in those cases with results for at least 4 patients (for each pairwise comparison only those patients with measures in both visits could be compared). No statistically significant differences were found in any of the comparisons with baseline.

[figure not shown]
Table 41. Barthel Index: Comparison between visits and baseline

	N	Mean (SD)	Median (Min-Max)	p-value ¹
Barthel Index(baseline)				
Barthel Index(cycle 2 d1)				
Barthel Index(baseline)				
Barthel Index(cycle 3 d1)				
Barthel Index(baseline)				
Barthel Index(cycle 4 d1)				
Barthel Index(baseline)				
Barthel Index(cycle 5 d1)				
Barthel Index(baseline)				
Barthel Index(cycle 6 d1)				
Barthel Index(baseline)				
Barthel Index(cycle 7 d1)				
Barthel Index(baseline)				

Barthel Index(cycle 8 d1)
Barthel Index(baseline)
Barthel Index(cycle 9 d1)
Barthel Index(baseline)
Barthel Index(cycle 10 d1)
Barthel Index(baseline)
Barthel Index(end of treatment)

1: Wilcoxon test

Figure 5. Barthel Index evolution

1.2. SAFETY ANALYSES

Every patient but one presented at least one adverse event during follow-up (n=xx, xx%). xx patients (xx%) presented at least one adverse event grade≥3 during follow-up. xx patients (x%) presented at least one toxicity (related AE) during follow-up. xx patients (xx%) presented at least one toxicity grade≥3 (related AE) during follow-up. xx patients (xx%) presented at least one SAE during follow-up, and none was reported as related to the treatment.

Table 42. Safety results summary

	N	%
AE	No	
	Yes	
	Total	
Adverse event grade≥3	No	
	Yes	
	Total	
Toxicity (any)	No	
	Yes	
	Total	
Toxicity grade≥3	No	
	Yes	
	Total	
SAE (any)	No	
	Yes	
	Total	
SAE related	No	
	Total	

1.2.1.

1.2.2. ADEVERSE EVENTS

The most frequent adverse event (any grade) were xxxxx (xx%, n=xx)....

Table 43. Frequencies of all adverse events

Adverse event	N	%
EXAMPLES:		
Neutrophil count decreased		
Fatigue		
Platelet count decreased		
Anaemia		
.....		

%: calculated respect the total number of patients (N=34)

The most frequent adverse events, (at least in 10% of the patients, n=xx), are reported in the following table:

Table 44. Most frequent adverse events

	N	%	
Specify Adverse events.	No	10	29.4%
	Yes	24	70.6%
EXAMPLE: Fatigue	Total	34	100.0%
.....	No	14	41.2%
	Yes	20	58.8%

Total	34	100.0%
--------------	----	--------

The most frequent adverse events with their respective grades are reported in the following table:

Table 45. Most frequent adverse events with grades

	No		G1		G2		G3		G4		Total	
	N	%	N	%	N	%	N	%	N	%	N	%

Specify Adverse events.

EXAMPLE: Fatigue

.....

1.2.2. TOXICITIES

The most frequent toxicities (related AE of any grade) were xxx decreased (xx%, n=xx)....

Table 46. Frequency of Toxicities

		N	%
Adverse event	Specify Advert event. EXAMPLE: Neutrophil count decreased		
		

%: calculated respect the total number of patients (N=xx)

The most frequent toxicities (at least in 10% of the patients, n=x), are reported in the following table:

Table 47. Most frequent Toxicities

		N	%
Specify Advert event EXAMPLE: Neutrophil count decreased	No		
	Yes		
	Total		
...	No		
	Yes		
	Total		

The most frequent toxicities with their respective grades are reported in the following table:

Table 48. Most frequent Toxicities with grades

	No		G1		G2		G3		G4		Total	
	N	%	N	%	N	%	N	%	N	%	N	%
Specify Advert event EXAMPLE: Neutrophil count decreased												
....												

1.2.3. SERIOUS ADVERSE EVENTS

Table 49. List of SAEs

Patient number	Hospital	AE grade	Relation	Intensity	Action	SAE (any)
1						
2	...					
3					

1.3. ANNEX I: LIST OF ALL TOXICITIES

Table 50. List of all toxicities

Patient number	Hospital	AE grade	Relation	Intensity	Action	SAE (any)
1						
2						
3						
4						
...						

1.4. ANNEX II: ADDITIONAL RESULTS

In the event that the study coordinator considered evaluating the variables of a subgroup of patients (those of interest for the article), for example patients with progression free survival longer than 9 months (**low survivors**), some tables and graphs (PFS and OS) could be required

1.4.1. LONG SURVIVORS

Table 51. Long survivors

	N	%
Long survivor (PFS≥9m)	No	
	Yes	
	Total	

x patients were considered long survivors and are listed below:

List of long survivor patients (PFS≥9 months)

Table 52. Long survivors

	Patient number	Time until PD/Exitus	Progression Free Survival	Time until Exitus	Overall survival
1					
2					
3					
4					
5					
6					
7					

1.4.2. BASELINE AND TUMOUR CHARACTERISTICS VS LONG SURVIVORS

Those variables reported in table 1 of the article are reported below stratified by long survivors.

Table 53. Baseline and tumour characteristic vs. long survivors

		Long survivor (PFS≥9m)			p-value
		No (n=27)	Yes (n=7)	Total (n=34)	
Age, mean +/-SD years	median (range)				
	mean (SD)				
Gender, n (%)	Male				
	Female				
KPS, n (%)	0				
	1				
	2				
Barthel Index, n=31	median (range)				
	mean (SD)				
MMSE, n=31	median (range)				
	mean (SD)				
Prior treatments, n (%)	Temozolomide				
	Nitrosoureas				
	Radiotherapy				
Tumor characteristics at first surgery					
Diagnosis, n (%)	Oligoastrocytoma				
	Grade 2				
	Grade 3				
	Oligodendroglioma				
	Grade 2				
	Grade 3				
	Unknown				
	Not reported				
Time from first AO diagnosis to first cycle, median (range) months	median (range)				
	mean (SD)				
Corticoids use during treatment, n (%)					

1: T-test for independent samples; 2: Mann-Whitney U test; 3: Fisher exact test.

